9.6 Reporting procedures concerning any deviations from primary statistical plan

In case of minor deviations from primary statistic analysis plan all deviations will be justified and described in final report for performance of the study. In case of changing of the statistical analysis plan correspondent amendment to the protocol will be issued.

9.7 Patients selection for assessment

Efficiency analysis will be performed on FAS population (Full Analysis Set), including all randomized patients taken at least one dose of the study product and having at least one efficiency assessment after Visit 2. Efficiency analysis in this population will be performed according to the assigned treatment.

Per protocol population (PP) includes all FAS population patients, went through all planned visits up to Visit 6, observing protocol conditions, namely patients, eligible to inclusion/non-inclusion criteria and finished participation in the study in accordance with all protocol requirements (except slight deviations from the protocol, which are not a cause for withdrawal from the study). Efficiency analysis in this population will be performed for confirmation of the

conclusions, obtained after efficiency assessment in FAS population.

List of major deviations from the protocol, caused patient withdrawal from the study or from PP population during statistical analysis, will be finalized by Sponsor before completion of statistical analysis and consequently will be presented in final study report. These protocol deviations may include but not limited to the following:

- Non-compliance with inclusion or non-inclusion criteria by the patient participating in the study.
- Participation of the patient in the study having exclusion criteria according to the study protocol;
- Incorrect study product administration schedule and dosage;
- Administration of the medicines, forbidden by the protocol

All randomized patients, receiving test product/comparator product, at least once, will constitute population for safety assessment. Safety assessment will be performed based on the actual treatment received by the patients. All AE revealed during the study should be included into analysis.

9.8 Efficiency assessment

Efficiency assessment of mean daily, mean daytime and mean nighttime number of urinary incontinence episodes / urination at the Week 2, 4, 8 and 12 Visits, including analysis based on primary efficiency criteria, as well as mean number of urinary incontinence episodes per week at the Week 12 – will be performed with the use of covariance analysis (ANCOVA). Number of urinary incontinence episodes / urination at the Visit of start of therapy will be used as covariate, and therapy group will be used as factor. Primary efficiency analysis according to primary efficiency criteria will be performed in FAS and PP populations. For evaluation of hypothesis of “non-inferior” efficiency upper border of one-side 95% confidence interval for difference in evaluation of mean daily number of urinations among test product and control product tolterone will be calculated. During comparison of therapy groups according to other efficiency criteria two-sided 95% confidence intervals will be built. Comparison of therapy groups on efficiency criteria: change in Overactive Bladder Awareness Tool Questionnaire (OAB Awareness Tool) and change in Quality of life by Quality of life Questionnaire EQ-5D will be performed following data validation concerning their normality, distribution using Kolmogorov-Smirnov criteria. In case of normal distribution data will be compared using Student’s t-test, otherwise non-parametric Mann-Whitney criteria will be used.

Primary efficiency analysis according to secondary efficiency criteria will be performed in FAS and PP populations.

Kolmogorov-Smirnov test for normal distribution and heterogeneous dispersion test using Leven criteria will be also performed during every visit as additional assessments in FAS population for mean daily, mean daytime and mean nighttime number of urinations and urinary incontinence episodes at Weeks 2, 4, 8 and 12. In case when one of these tests is apparently statistically significant ($p < 0.05$), comparison between therapy groups will be performed using non-parametric Mann-Whitney criteria.

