1.2 Study centers and investigators

Investigation will be performed in 15 urological centers within the territory of the Russian Federation and the Belarus Republic.

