4.3 Description of measures providing subjectivity minimization

4.3.1 Randomization

For exception of subjectivity in study product prescription randomization process is provide with use of envelopes without any additional stratification.

Overall 300 patients are planned to be randomized, that will give at least 222 patients completely finished the study (111 patients per study group).

Patients will be randomly assigned into two groups:

1. Uritos[®] (Imidafenacin, film-coated tablets; 0,1 mg, Kyorin Pharmaceutical Co. Ltd., Japan), oral, 1 tablet BID after meals (after breakfast and after supper).
2. Urotol[®] (tolterodine, film-coated tablets; 2 mg, Zentiva k.s., Czech Republic), oral, 1 tablet BID after meals (after breakfast and after supper).

Randomization is performed in 1:1 ratio. List of randomization numbers will be generated beforehand by Sponsor's data processing department or designated Contract research organization (CRO) using correspondent software package.

Sponsor will provide all research centers with the set of enumerated sealed envelopes. Each envelop contains randomization number and prescribed medicinal product. Envelopes will be sequentially numbered.

Patients, familiarized with the Patient's information list and signed Informed consent form, will be assigned numbers in order of research center visiting for screening procedures performance. During randomization visit (treatment start visit) each patient following screening and satisfying inclusion/non-inclusion criteria will be assigned unique randomization number: Investigator takes the subsequent envelop (sequentially at order of magnitude) and assigns randomization number to the patient according to the number contained in the envelope with correspondent fixation in primary documentation, CRF and Screening/patients inclusion log. Hereafter list of randomization numbers will be included into primary study file and final study report.

Randomization will be balanced around research centers so that one center would contain approximately equal number of patients, receiving test product and comparator product.

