9.2 Patient population justification

H_0 (null hypothesis): effect of Urotol (tolterodine) according to assessment of mean daily urination episodes exceeds effect of Uritos[®] (Imidafenacin) with non inferiority threshold 0.8 episodes per day.

H_1 (alternative hypothesis): effect of Uritos[®] (Imidafenacin) according to assessment of mean daily urination episodes exceeds effect of Urotol (tolterodine) with non inferiority threshold 0.8 episodes per day.

$H_0: \mu_A - \mu_B \geq \delta$ $H_1: \mu_A - \mu_B < \delta$,

where μ_A, μ_B – efficiency of medicinal products Uritos[®] (Imidafenacin) and Urotol (tolterodine), respectively; δ – non-inferiority threshold ($\delta = 0,8$ episodes per day)

Following levels of error of the first kind = 0.025 and error of the second kind = 0.2 were taken for calculation of the study sample (that corresponds to 80% power of the study), acceptable non-inferiority threshold at the primary endpoint at Week 12 - 0.8 episodes per day; based on results of previous examination of imidafenacin, standard deviation at the primary endpoint is considered to be 2.12 episodes per day on sample consisting from 355 patients.

Sample size calculation is based on formula from [36]:

$$n_A = \frac{(r+1)\sigma^2(Z_{1-\beta} + Z_{1-\alpha})^2}{r((\mu_A - \mu_B) - \delta)^2}$$

Where $r = n_A/n_B$,

σ – assumed standard deviation for change in mean daily number of urination episodes.

n_A, n_B – study group and control group sizes, respectively.

μ_A, μ_B – assumed mean change of mean daily urination episodes in study group and control group, respectively.

$Z_{1-\alpha}, Z_{1-\beta}$ – cumulative function parameters of normal standard distribution for first (α) and second (β) types of errors, respectively.

δ – non-inferiority threshold.

With due consideration of homogeneous distribution of patients among treatment groups ($n_A = n_B$ if $r = 1$), in each treatment group will be randomized

$$n = \frac{2 \cdot 2.12^2 (0.84 + 1.96)^2}{0.02} = 111$$

Sample containing 222 patients (111 per study group) is considered to be sufficient for proof of alternative hypothesis (rejection of null-hypothesis) at the significance level 0.025% and study strength 80%. With due consideration of withdrawal during treatment total amount of patients to be randomized is about 300 (150 patients per study group).

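### If allocation is balanced by centre, as one sentence of section 4.3.1 says, leaving centre out of the section 9.8 ANCOVA forgoes precision wherever centres differ

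*Combined protocol and SAP*

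**What the plan says.** Section 1.2 gives the number of sites: "Investigation will be performed in 15 urological centers within the territory of the Russian Federation and the Belarus Republic". The synopsis says around 15.

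Section 4.3.1 makes two statements about allocation that do not sit easily together. It opens by saying that the "randomization process is provide with use of envelopes without any additional stratification". Its closing paragraph says: "Randomization will be balanced around research centers so that one center would contain approximately equal number of patients, receiving test product and comparator product". The ratio is 1:1. Centres receive sequentially numbered sealed envelopes, but no block size or centre-specific list is described.

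Section 9.8 analyses the primary endpoint and the other diary counts by ANCOVA. The count "at the Visit of start of therapy will be used as covariate, and therapy group will be used as factor". No centre or country term appears anywhere in section 9, and no between-centre variance is given.

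**The concern.** A variable used to balance the allocation normally belongs in the analysis model. When arms are balanced within centres, differences between centres largely cancel from the treatment comparison. A model without centre still counts those differences as residual error, so its standard error is larger than the true sampling variability of the estimate.

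Differences between centres are plausible here. The endpoint is a patient diary count, investigators explain the diary rules and check the entries at each visit (sections 4.5.3 and 7.2), treatment is open-label (section 4.3.2), and drug-free methods are allowed with no standardisation stated (section 6.2). How large the differences are is unknown.

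What is at stake is precision of the non-inferiority bound. The choice also has to be made in advance, because adding centre after open-label data have been seen would look data-driven.

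**Working it through.** **Inputs.** From section 9.2: margin 0.8, SD 2.12, one-sided alpha 0.025, power 80%, 111 evaluable per group, about 300 randomised. From section 1.2: 15 centres. Assumed, because the documents give no value: the ICC, meaning the share of residual variance after baseline that lies between centres. The SD of 2.12 is used as the residual SD, since no baseline correlation is given. The width ratio below does not depend on it.

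**Plan's own figure.** n per group = 2 × 2.12² × (0.84 + 1.96)² / 0.8² = 2 × 4.4944 × 7.84 / 0.64 = 110.1, so 111. This reproduces the plan. (The denominator reads 0.02 in the text available to me, which would give 3,524; I take that as a text-extraction fault and do not rely on it.)

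**Formulas under within-centre balance.**
- Model SE without centre: 2.12 × sqrt(2/111) = 0.2846. Half-width: 1.96 × 0.2846 = 0.558.
- SE with centre, which is also the true sampling SE under balance: 0.2846 × sqrt(1 − ICC).
- Power with centre: Φ(0.8/SE_true − 1.96).
- Power without centre: Φ((0.8 − 0.558)/SE_true).
- Actual one-sided error without centre: Φ(−0.558/SE_true).

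Example at ICC 0.10: SE_true = 0.2846 × 0.9487 = 0.270 and the half-width with centre is 0.529. Power is Φ(2.963 − 1.96) = 84.2% with centre and Φ(0.242/0.270) = 81.5% without. Actual error without centre is Φ(−2.066) = 0.0194.

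| Assumed ICC | Half-width with centre | Excess width without centre | Power without / with centre | Actual error without centre |
|---|---|---|---|---|
| 0 | 0.558 | 0% | 80.3 / 80.3% | 0.0250 |
| 0.05 | 0.544 | 2.6% | 80.9 / 82.2% | 0.0222 |
| 0.10 | 0.529 | 5.4% | 81.5 / 84.2% | 0.0194 |
| 0.20 | 0.499 | 11.8% | 82.9 / 88.2% | 0.0142 |

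**Simulation check.** 15 centres of 15 patients, 20,000 runs per row, t-intervals. Each cell gives the model without centre, then with centre.

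| Allocation | ICC | Mean half-width | One-sided error | Power |
|---|---|---|---|---|
| Balanced by centre | 0 | 0.558 / 0.559 | 0.0258 / 0.0256 | 80.5 / 80.2% |
| Balanced by centre | 0.05 | 0.557 / 0.545 | 0.0217 / 0.0247 | 81.0 / 82.0% |
| Balanced by centre | 0.10 | 0.556 / 0.531 | 0.0193 / 0.0238 | 81.7 / 84.2% |
| Not balanced | 0 | 0.558 / 0.576 | 0.0222 / 0.0225 | 80.1 / 77.5% |
| Not balanced | 0.05 | 0.557 / 0.562 | 0.0254 / 0.0256 | 80.6 / 79.9% |
| Not balanced | 0.10 | 0.556 / 0.547 | 0.0250 / 0.0251 | 80.2 / 81.5% |

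The balanced rows agree with the formulas. In the unbalanced rows the model without centre is not miscalibrated: its error stays at about the nominal level, apart from simulation noise. There a centre term helps only once the ICC is large enough to pay for chance imbalance within centres. At ICC 0 it widens the interval by 0.576/0.558 − 1, about 3%.

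**The case against.** A reader might infer that the planned interval simply is too wide. The documents do not support that without conditions. It requires centre variance that remains after baseline adjustment, for which they give no figure, and within-centre balance, on which section 4.3.1 speaks both ways. The two sentences can be read together as balance by centre and nothing further, but the section gives no per-centre list or block size that would settle it. This objection stands, and it is why the point is conditional.

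A reader might also infer that the trial is underpowered or its conclusion unsafe. Neither follows. Section 9.2 sizes the trial on the full SD with no deduction for centre, so power without centre is 80.3% or more throughout the formula table. What is given up is a gain beyond the plan. Actual error falls below 2.5%, which is conservative.

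Three further objections narrow the point without removing it:
- Section 9.8 sets the bound from a one-sided 95% interval, whereas section 9.3 and the synopsis say 97.5%. At 95% the half-width is 1.645 × 0.2846 = 0.468, 16% narrower than 0.558; a centre term would need an ICC of about 0.30 to match that. This is a separate and larger defect, acting in the anti-conservative direction. Correcting it leaves the centre question open.
- Falling from 300 randomised to 222 evaluable is a 26% loss, which would partly undo the balance within centres. The balanced figures are therefore the upper end of the effect.
- Section 9.8 switches to Mann-Whitney when the normality or variance test is significant. A centre term in the ANCOVA does not reach that comparison.

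**Conclusion.** The point holds conditionally, as a matter of efficiency. If allocation is balanced by centre and centres differ after baseline adjustment, omitting centre overstates the standard error by about 1/sqrt(1-ICC). For an assumed ICC up to 0.10, that is at most 5.4% of the half-width and just under 3 power points; at 0.20 it is 11.8% and just over 5 points; at zero nothing is lost. At an ICC of 0.10 the precision is worth about 11 patients per arm (0.90 × 110.1 = 99.1, so 100 instead of 111).

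The result rests on the assumed ICC, on roughly equal centres and on arms staying balanced within centres at analysis. If allocation is not balanced by centre, the model in section 9.8 keeps its nominal error rate. The inconsistency within section 4.3.1 needs resolving in either case.

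**What to change.** 1. In section 4.3.1, reconcile the opening and closing statements so that the text says whether allocation is stratified by centre and, if so, how the lists are built.
2. If it is stratified by centre, add centre as a factor to the section 9.8 ANCOVA for the primary and other diary endpoints. Add a rule for pooling small centres within country, fixed before database lock. On average 222/15 leaves about 15 evaluable patients per centre, roughly 7 per arm, so some sites may well need pooling. The documents give no basis for a particular threshold, so the sponsor should choose and justify one.
3. State whether the Mann-Whitney fallback also takes account of centre.

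The cost is a protocol amendment, since section 9.6 requires one when the analysis plan changes, and about 14 degrees of freedom out of roughly 220. No new data are needed. With balance and no centre variance the interval widens by about 0.2% (0.558 to 0.559). The penalty of about 3% arises only if centre is added although allocation was not balanced by centre and centre variance is nil, which is why step 1 comes first.

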	
Sample containing 222 patients (111 per study group) is considered to be sufficient for proof of alternative hypothesis (rejection of null-hypothesis) at the significance level 97.5% and study strength 80%. With due consideration of withdrawal during treatment total amount of patients to be randomized is about 300 (150 patients per study group).
 
For treatment efficiency assessment (primary endpoint) one-side 97.5% confidence interval for arithmetic mean values of primary endpoint will be calculated. In other cases of comparison two-sided 95% confidence intervals will be utilized.
 
Changes will be considered as significant at $p < 0.05$.
 
For comparison of AE appearance in the study groups χ^2 test of exact Fisher test is planned to be applied, for comparison of manifestation rate Mann-Whitney U test will be applied.
 
Laboratory parameters (total blood count and blood biochemistry, urinalysis), vital parameters will be assessed separately to each group with the following comparison using paired Student t-test for connected samples (for parameters with normal distribution) or using non-parametric Wilcoxon signed rank test for connected samples (for parameters with ordinary scale type or in case of significant distribution deviations from normal).

--	--

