9.3 Significance level applied

All analysis types used in the study will be performed at the statistical significance level < 0.05 if otherwise noted.

During assessment of significance of discrepancies in primary endpoint access one-sided 97.5% confidence interval will be applied.

Two-sided 95% confidence intervals will be applied during description and testing of other data.

9.4 Interim analysis and study cessation criteria.

Not applicable

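### Section 9.8 judges non-inferiority on a one-sided 95% limit, while section 9.3, the synopsis and the sample size use one-sided 97.5%; following 9.8 doubles the false non-inferiority rate from 2.5% to 5%

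*Combined protocol and SAP*

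**What the plan says.** The level of the primary non-inferiority test appears in four places in the combined protocol and SAP.

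- **Section 9.8 (Efficiency assessment)** names the model (ANCOVA with the baseline count as covariate and treatment group as factor) and the populations (FAS and PP). It bases the non-inferiority decision on the "upper border of one-side 95% confidence interval for difference in evaluation of mean daily number of urinations". Its next sentence assigns two-sided 95% intervals to the other efficiency criteria.
- **Section 9.3 (Significance level applied)** says: "During assessment of significance of discrepancies in primary endpoint access one-sided 97.5% confidence interval will be applied". Its general default for other analyses is 0.05.
- **Section 1.3 (synopsis)** says that a "one-side 97.5% confidence interval for arithmetic mean values of primary endpoint will be calculated".
- **Section 9.2 (sample size)** says: "Following levels of error of the first kind = 0.025 and error of the second kind = 0.2 were taken for calculation of the study sample". The worked calculation there uses 1.96 as the normal quantile for alpha. The synopsis repeats the 0.025.

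This is all current text, not a description of superseded wording. No section says which statement governs.

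**The concern.** The level of the confidence limit decides whether this trial succeeds. Section 9.8 is the section a statistical programmer would work from, because it is the only one that gives the model, covariate, populations and bound together. Read literally, it sets a one-sided 5% test where the trial was designed for 2.5%.

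Two features add to the exposure. The study is open-label (section 4.3.2), and the randomisation list is known to the investigators and the sponsor (section 4.8). With two levels already in the plan, the choice between them could be made, or could appear to have been made, after results are known. The study is also meant to support registration (section 2). A non-inferiority claim that passes under one section and fails under another can be challenged whichever section is used.

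**Working it through.** **Inputs**

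- Margin: "acceptable non-inferiority threshold at the primary endpoint at Week 12 - 0.8 episodes per day" (section 9.2).
- SD: "standard deviation at the primary endpoint is considered to be 2.12 episodes per day on sample consisting from 355 patients" (section 9.2).
- Power 80%, so z = 0.8416; the document rounds this to 0.84.
- Allocation 1:1 (section 4.3.1).
- True difference 0. No number is stated, but the synopsis formula has no difference term, so zero is implied.
- 111 evaluable and 150 randomised per arm (section 9.2).

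**1. Reproduce the plan's sample size**

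n per arm = 2 × SD² × (z_alpha + z_beta)² / margin²

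- One-sided 0.025, document's rounded quantiles: 2 × 2.12² × (1.96 + 0.84)² / 0.8² = 8.9888 × 7.84 / 0.64 = 110.1, so **111**. Unrounded quantiles give 110.2, also 111. This matches the plan.
- One-sided 0.05: 8.9888 × (1.6449 + 0.8416)² / 0.64 = 86.8, so **87**. This does not match.

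The design was therefore built on 0.025. (The denominator in section 9.2's worked line reads 0.02 in the text available here, possibly a file-conversion fault; 111 requires 0.8² = 0.64.)

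**2. Type I error at the margin**

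Non-inferiority is declared if d + z × SE < 0.8, where d is the observed difference, Uritos minus Urotol. At a true difference of 0.8 the probability of this is Φ(−z):

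- z = 1.96 (section 9.3): 0.025
- z = 1.645 (section 9.8): 0.050

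This contrast does not depend on the SD or the sample size.

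**3. Largest observed difference that still passes**

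Limit = 0.8 − z × SE, with SE = 2.12 × √(2/n). SE is 0.2846 at 111 per arm and 0.2448 at 150.

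| n per arm | Limit, 97.5% (9.3) | Limit, 95% (9.8) | Width of conflict | Power at true difference 0, 97.5% | Power at true difference 0, 95% |
|---|---|---|---|---|---|
| 111 | 0.242 | 0.332 | 0.090 | 80.3% | 87.8% |
| 150 | 0.320 | 0.397 | 0.077 | 90.5% | 94.8% |

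**4. How often the two rules disagree**

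- True difference 0: 87.8 − 80.3 = 7.5% of trials at 111 per arm; 94.8 − 90.5 = 4.3% at 150.
- True difference at the margin: 5.0 − 2.5 = 2.5%.
- True difference midway between the two limits: the limits lie 1.960 − 1.645 = 0.315 SE apart, so the probability of landing between them is 2Φ(0.1575) − 1, about 12.5% at either sample size.

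**The case against.** The strongest reply is that the intended level is obvious. The synopsis, section 9.2 and section 9.3 all point to 0.025; section 9.3 exists to set the level and addresses the primary endpoint explicitly; and the sample size works only at 0.025. If those govern, the error rate stays at 2.5%. That is correct, and the doubling is conditional on section 9.8 being followed. But agreement elsewhere shows how to correct 9.8; it does not stop an analyst applying 9.8 as written. Nor can its wording safely be taken as loose language for a two-sided 95% interval, because its next sentence uses the two-sided term for the other criteria.

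Four smaller points stand in part.

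- **The limits are illustrative.** They use the unadjusted SD of 2.12, whereas 9.8 specifies ANCOVA and the documents give no residual SD. If baseline explained 10% to 30% of the variance (an assumption), the limits at 111 per arm would be about 0.27 to 0.33 under 9.3 and 0.36 to 0.41 under 9.8. The contrast of 5% with 2.5% would not change.
- **The zone of conflict is narrow,** under 0.1 episodes per day. Even so, two drugs with identical effects would land in it in 4.3% to 7.5% of trials.
- **Section 9.6** requires an amendment for changes to the analysis plan. That does not settle which of two levels already in the plan applies, and the same section lets minor deviations be justified in the final report.
- **The synopsis wording is looser.** It refers to mean values of the endpoint, not to the difference between arms, so it supports the level but not the full decision rule. The clean conflict is between 9.8 and sections 9.2 and 9.3.

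**Conclusion.** The concern holds. The primary decision rule is stated at two levels in current text, and the section that specifies the test carries the one that does not match the design. Following section 9.8 gives a one-sided type I error of 5.0% at the margin against the planned 2.5%, whatever the SD. For observed differences of 0.242 to 0.332 episodes per day at 111 per arm, or 0.320 to 0.397 at 150, the trial's conclusion depends on which section is used. Those ranges assume an SD of 2.12 in both arms, a normal approximation and no covariate adjustment. This must be settled before analysis, because it fixes the confirmatory result.

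**What to change.** In section 9.8, replace the one-sided 95% interval with a one-sided 97.5% interval (equivalently, the upper limit of the two-sided 95% interval) for the ANCOVA-adjusted difference, Uritos minus Urotol. State that non-inferiority is concluded only if that limit lies below 0.8 episodes per day.

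In the same edit, correct two clerical slips: the synopsis gives the significance level as 97.5%, and section 9.2 gives it as 0.025%. Both should read one-sided 0.025. They do not change the decision rule.

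The cost is one sentence and two wording corrections. No design change and no extra patients are needed, because 111 per arm already assumes 0.025. The correction should be documented before any outcome data are analysed.
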